4.2 OTHER TREATMENTS, EMERGENCY PROCEDURES, RESTRICTIONS

4.2.1 Other treatments and emergency procedures

Patients should keep their existing therapies as stable as possible, particularly their therapy with either ACEi or ARB, from screening at Visit 1 until the end of follow-up at Visit Follow-up 2 (FUp2).

New therapies should only be initiated if necessary for medical reasons. Please see the inclusion / exclusion criteria ([sections 3.3.2](#) and [3.3.3](#) respectively) and [Table 4.2.2.1: 1](#) for full details of restrictions.

If a patient has an adverse event that the Investigator believes may be related to trial medication (either empagliflozin and/or BI 690517) then the Investigator may interrupt the medication. Trial treatment may be restarted at any time after a temporary reason for treatment discontinuation if medically justified (see [section 3.3.4.1](#)).

Background therapies (ACEi/ARB) or any other standard of care medications are not considered part of the clinical trial supplies, and therefore will not be provided.

There are no special emergency procedures to be followed.

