7.2.6 Safety analyses

Adverse events will be coded using the Medical Dictionary for Drug Regulatory Activities (MedDRA). Standard BI summary tables and listings will be produced. All adverse events with an onset between start of treatment and end of the REP, a period of 7 days after the last dose of trial medication, will be assigned to the on-treatment period for evaluation.

All treated patients will be included in the safety analysis based on their actual treatments. In general, safety analyses will be descriptive in nature and will be based on BI standards. No hypothesis testing is planned.

Statistical analysis and reporting of adverse events will concentrate on treatment-emergent adverse events, i.e. all adverse events occurring between start of treatment and end of the REP. Adverse events that start before first drug intake and deteriorate under treatment will also be considered as 'treatment-emergent'. Adverse events will be summarised by the treatment at which the subject was randomised, and the treatment at the onset of AE for the drug-related AE.

Frequency, severity, and causal relationship of adverse events will be tabulated by system organ class and preferred term after coding according to the current version of the Medical Dictionary for Drug Regulatory Activities (MedDRA).

Summary of participants with down-titration due to AE will be provided separately. Adverse event of special interest (AESI) and other specific AEs with collection of additional information in the eCRF (which include hyperkalaemia) will be summarised as well. Analysis of serum potassium will further include change from baseline, the incidence of serum potassium levels of 5.6 mmol/L or higher and higher than 6.0 mmol/L.

Laboratory data will be analysed both quantitatively as well as qualitatively. The latter will be done via comparison of laboratory data to their reference ranges. Values outside the reference range as well as values defined as clinically relevant will be summarised. Treatment groups will be compared descriptively with regard to distribution parameters as well as with regard to frequency and percentage of patients with abnormal values or clinically relevant abnormal values.

Vital signs, physical examinations, or other safety-relevant data observed at screening, baseline, during the course of the trial and at the end-of-trial evaluation will be assessed with regard to possible changes compared to findings before start of treatment.

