Run-in	Placebo, Empagliflozin, respectively	Date / time of first administration of empagliflozin / placebo	For patients discontinue in Run-in Period, 12:00 a.m on the day after last administration of empagliflozin / placebo + REP (7 days),

			For patients continue in Treatment Period, 12:00 a.m on the day after last administration of empagliflozin / placebo + REP (7 days) or first administration of BI 690517 / placebo, whichever occurs first
On-treatment	Placebo, BI 690517, Plus Empagliflozin or matching placebo, respectively	Date / time of first administration of BI 690517 / placebo	12:00 a.m on the day after last administration of BI 690517 / placebo + REP (7 days) Or 12:00 a.m on the day after patient's trial termination date,
Follow-up ¹	F/U Placebo, F/U BI 690517, plus Empagliflozin or matching placebo, respectively	12:00 a.m on the day after last administration of BI 690517 / placebo + REP (7 days)	12:00 a.m on the day after patient's trial termination date

¹ Follow-up phase might not exist, e.g. if the patient's trial termination date is within 7 days after last administration of study drug

In the case that the patient is permanently discontinued BI 690517, but is continuing on Empagliflozin during Treatment Period, the occurrence of AEs between REP of BI 690517 and REP of Empagliflozin will be provided in the listing. For treatment interruptions, the occurrence of AEs between the start of interruption and re- start of treatment will be assigned to actual treatment received. These cases will be flagged in the safety listings as occurring during the off-treatment period. AEs will be displayed by dose group and will be provided in the CTR.

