7.8.1 Adverse Events

Analyses of AEs will be descriptive in nature. All analyses of AEs will be based on the number of patients with AEs and NOT on the number of AEs.

Furthermore, for analysis of AE attributes such as duration, severity, etc. multiple AE occurrence data on the CRF, will be collapsed into AE episodes provided that all of the following applies:

- The same MedDRA lowest level term was reported for the occurrences
- The occurrences were time-overlapping or time-adjacent (time-adjacency of 2 occurrences is given if the second occurrence started on the same day or on the day after the end of the first occurrence)
- Treatment did not change between the onset of the occurrences OR treatment changed between the onset of the occurrences, but no deterioration was observed for the later occurrence

For further details on summarisation of AE data, please refer to "Analysis and presentation of adverse event data from Clinical Trials" [\(9\)](#) and "Handling of missing and incomplete AE da [\(4\)](#).

The analysis of AEs will be based on the concept of TEAEs. That means that all AEs occurring between the first drug intake until 7 days after last drug intake will be assigned to

actual treatment groups. All AEs occurring before first drug intake of empagliflozin/ placebo will be assigned to ‘screening’ and all AEs occurring after EoT + 7 days will be assigned to ‘follow-up’ (for listings only). AEs that start before first drug intake and during Run-in Period and deteriorate under treatment will also be considered as ‘treatment-emergent’. For details on the treatment definition, see [Table 6.1:1](#) in [Section 6.1](#).

If only the start date of an AE is collected (without start time), any AE occurrence on the same day as the first empagliflozin or BI 690517 administration will be assigned to the run-in or on-treatment phase, respectively. In addition, a summary of patients with down-titration due to AE will be provided.

An overall summary of AE will be presented for treated set during Run-in and on-treatment periods, respectively. This will show the number and percentage of patients with any AE, severe AEs, any investigator defined drug-related AEs, AEs of Special Interest (AESIs), AEs leading to the discontinuation of empagliflozin or BI 690517, and down-titration (dose reduction) of BI 690517, and serious AEs (SAEs).

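### SAP Table 6.1:1 closes the on-treatment AE phase 7 days after the last BI 690517/placebo dose even when empagliflozin/placebo continues, which does not match SAP 7.8.1 or the natural reading of protocol 7.2.6

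*SAP*

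**What the plan says.** - **SAP 6.1, Table 6.1:1.** The on-treatment phase starts with the first BI 690517/placebo dose and ends at "12:00 a.m on the day after last administration of BI 690517 / placebo + REP (7 days"). The only alternative end is trial termination. The follow-up phase starts at that same BI-anchored moment. Empagliflozin is not part of the end rule.
- **SAP 6.1, text below the table.** The case of a patient who stops BI 690517 permanently and continues empagliflozin is named: "the occurrence of AEs between REP of BI 690517 and REP of Empagliflozin will be provided in the listing".
- **Protocol 7.2.6.** AEs with onset from the start of treatment to the end of the residual effect period (REP), "a period of 7 days after the last dose of trial medication, will be assigned to the on-treatment period for evaluation".
- **SAP 7.8.1.** Assigned to the actual treatment groups are "all AEs occurring between the first drug intake until 7 days after last drug intake". The section adds that "all AEs occurring after EoT + 7 days will be assigned to" follow-up, which is for listings only. It then says "For details on the treatment definition, see" Table 6.1:1.
- **SAP section 4.** No change from the protocol's planned analysis is declared.
- **Protocol 3.3.4.1 and 4.2.1.1.** After the second randomisation a patient who permanently stops one product may continue the other and should keep to the visit schedule.
- **Protocol 6.2.5.** An early EoT visit in the Treatment Period is for patients who have stopped both products.

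**The concern.** Stopping BI 690517 while empagliflozin/placebo continues is a planned path. The potassium and cortisol rules in protocol 3.3.4.1 stop BI 690517/placebo only. For these patients Table 6.1:1 and SAP 7.8.1 give different end dates, and the table also departs from what protocol 7.2.6 most naturally means. Two programmers could produce different AE tables from the same data, and both could cite the SAP.

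If the table is followed, AEs that arise more than 7 days after BI 690517 stops are missing from the patient counts, although the patient is still taking a randomised product. SAP 7.8.1 promises on-treatment tables of AEs related to empagliflozin or BI 690517, and of discontinuations of either product due to AEs. Under the table's window, an empagliflozin-related AE or an empagliflozin discontinuation in this period cannot be counted there. The tables are N (%) of patients, and the SAP describes no exposure adjustment. An arm with more BI-only stops therefore has less time in which an AE can be counted.

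**Working it through.** The plan states no figure on this point, so there is nothing to reproduce. The check compares the end rules by date, then illustrates the effect.

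**Inputs from the documents.** EoT is Day 99 and FUp1 is Day 106 (protocol flow chart). The REP is 7 days for empagliflozin (protocol 1.2.2) and 7 days for BI 690517 (SAP 6.1).

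**Step 1: one AE under three rules.** Suppose BI 690517 is stopped on Day 43, empagliflozin is taken to Day 99, and an AE starts on Day 70.

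| Rule | End of window | AE on Day 70 |
|---|---|---|
| Protocol 7.2.6, last dose of either product + 7 | 99 + 7 = Day 106 | tabulated |
| SAP 7.8.1, EoT + 7 | 99 + 7 = Day 106 | tabulated |
| SAP Table 6.1:1, last BI 690517/placebo dose + 7 | 43 + 7 = Day 50 | listed only |

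**Step 2: time removed per patient.** For a BI-only stop on day d, the time lost is 106 − (d + 7) = 99 − d days out of 106.

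| Stop day | Days lost | Share of 106 |
|---|---|---|
| 8 | 91 | 86% |
| 15 | 84 | 79% |
| 43 | 56 | 53% |
| 71 | 28 | 26% |

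**Step 3: illustration of the effect on tabulated risk.** The documents give neither BI-only stop rates by arm nor AE risks, so everything in this step is assumed. The AE hazard is constant and the same in every arm, before and after BI 690517 stops, with risk p over 106 days, so λ = −ln(1 − p)/106. A fraction f of the arm stops BI 690517 only, spread equally over Days 8, 15, 43 and 71, and continues the other product to Day 99.

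Tabulated risk = (1 − f) × p + f × mean[1 − exp(−λ(d + 7))]

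For p = 30%, λ = 0.3567/106 = 0.003365 per day. With d + 7 = 15, 22, 50 and 78, the four terms are 4.9%, 7.1%, 15.5% and 23.1%, with mean 12.66%.

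- f = 5%: 0.95 × 30% + 0.05 × 12.66% = 29.1%
- f = 20%: 0.80 × 30% + 0.20 × 12.66% = 26.5%

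| True risk p | f = 5% | f = 10% | f = 20% | Patients missing of 60 at f = 20% |
|---|---|---|---|---|
| 10% | 9.7% | 9.4% | 8.8% | 0.7 |
| 30% | 29.1% | 28.3% | 26.5% | 2.1 |
| 60% | 58.4% | 56.8% | 53.7% | 3.8 |

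The last column is 60 × (p − tabulated risk), using unrounded risks. The loss is proportional to f.

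**The case against.** The best defence is that Table 6.1:1 is a deliberate exposure window for BI 690517, the drug whose doses are under study.

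- **The protocol term is not uniform.** Protocol 4.2.1 glosses it as both products: "related to trial medication (either empagliflozin and/or BI 690517"). But SAP 6.7, citing protocol 2.2.2, defines baseline UACR from week -2 up to the first intake of trial medication. Empagliflozin/placebo starts at week -8, so there the term can only mean BI 690517. The Treated Set is also defined by BI 690517 or its placebo. This stands: the conflict is with the natural reading of 7.2.6, not with an unambiguous rule.
- **SAP 7.8.1 points back to the table** and does not name the drug in its 7-day window. This stands and softens the conflict, but the EoT + 7 start of follow-up still differs from the table.
- **The convention is used elsewhere.** For the same patients, SAP 7.8.2 and 7.8.3 take EoT for laboratory and vital-sign data from the nearest scheduled visit on BI 690517. This supports intent, though neither section governs AEs.
- **The wider window has an attribution problem.** It counts under a BI 690517 dose group AEs that arise weeks after that drug was stopped. This stands, and is a reason to show both windows.

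A reader might go further and infer that these AEs disappear from the report. They do not. They are collected and listed. Ketoacidosis, like hypotension, hyperkalaemia, adrenal insufficiency and acute kidney injury, also has a separate summary from special eCRF pages, for which SAP 7.8.1 states no on-treatment limit. Nor are these all AEs on active drug: on the placebo background the continuing product is placebo.

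**Conclusion.** The end rules conflict in the current text, and SAP section 4 does not record the table's BI-anchored window as a choice. The mismatch with the EoT + 7 rule in SAP 7.8.1 remains even if the protocol's wording is read as BI 690517 only. So does the gap in the on-treatment tables of empagliflozin-related AEs and empagliflozin discontinuations.

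The direction follows from the rule: an arm with more BI-only stops loses more tabulated time. The size is modest at the assumed rates and cannot be derived from the documents. It rests on the assumed stop fraction, stop days, constant hazard and AE risk.

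A reader might infer that the higher doses will look safer. The documents do not support that as a finding. Protocol 4.1.2 reports a numerical rise in potassium change with dose in an earlier study, which makes dose-related stops plausible, but no stop rates are given. Several other stopping rules in protocol 3.3.4.1 end all treatment, down-titration is available for some potassium elevations, and continuing the other product is optional. The safety analysis is descriptive with no hypothesis testing, and AE presentation also follows a sponsor standard that is not among the documents.

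**What to change.** 1. Reconcile Table 6.1:1, SAP 7.8.1 and protocol 7.2.6 to one stated end rule that names the product or products whose last dose counts. State it for both the empagliflozin and the placebo background.
2. Tabulate key AEs under both windows, each labelled: to 7 days after the last dose of either trial product, and to 7 days after the last BI 690517/placebo dose. Key AEs here are all AEs, SAEs, AESIs, empagliflozin-related AEs and empagliflozin discontinuations due to AEs.
3. If the BI-anchored window remains the main one, record it in SAP section 4 as a change.

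The cost is SAP wording and one extra set of tables. The wider window includes AEs that arise after BI 690517 was stopped, and it differs from the BI-anchored EoT used for laboratory and vital-sign data. Table footnotes should say so.

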6.2 IMPORTANT PROTOCOL DEVIATIONS

Handling of important protocol deviations (iPDs) in the analysis is included in the deviation (DV) domain specifications and stored within the Trial Master File (TMF) in the Electronic Document Management System (EDMS).

Consistency check listings (for identification of violations of time windows) and a list of protocol deviations (e.g. deviations in drug administration, in blood sampling times, etc.) will be provided for discussion at the Trial Oversight Meeting (TOM) prior to Data Base Lock (DBL) or at the Report Planning Meetings (RPMs). At these meetings, it will be decided whether a discrepant data value can be used in analyses or whether it must be corrected in the clinical database. Each protocol deviation must be assessed to determine whether it is an iPD. For definition of iPDs, and for the process of identification of these, refer to "Identify and Manage Important Protocol Deviations (iPD)".

If any iPDs are identified, they are to be summarised into categories and will be captured in the meeting minutes and additionally via an accompanying Excel spreadsheet. The iPDs may lead to exclusion of patients from analysis sets. The documentation of the iPD categories and

how to handle iPDs in the analysis is included in the DV domain specifications and stored within the TMF in EDMS. If the data show other iPDs, this domain will be supplemented accordingly. iPDs will be summarised during both Run-in and Treatment Period for randomised set, and iPDs of patients discontinued during Run-in Period will be provided by listings.

Non-important Corona Virus Disease 2019 (COVID-19) related PDs will only be listed.

6.3 SUBJECT SETS ANALYSED

In addition to the subject sets for statistical analysis defined in the CTP, Section 7.2.1, the following subject sets will be used:

Run-in Randomised Set (RIRS):

This patient set includes all randomised patients of the Run-in Period, regardless of being treated or not.

Run-in Treated Set (RITS):

This patient set includes all randomised patients of the Run-in Period who were documented to have taken at least one dose of empagliflozin or placebo.

Full Analysis Set (FAS):

[figure not shown]
This patient set includes all randomised patients who had at least one baseline measurement of UACR at week -2, -1, or 0 and at least one post-baseline measurement when patients are still on treatment of BI 690517. The FAS will be the main analysis set for the analysis of efficacy.

[Table 6.3: 1](#) illustrates the data sets which are to be used for each category class of endpoints.

Table 6.3: 1 Subject sets analysed

Class of endpoint	ES	RIRS	RITS	RS	TS	FAS	PKS
Disposition	X			X			
Exposure / Compliance			X		X		
iPDs				X			
Demographic/baseline		X		X			
Primary endpoint						X	
Secondary endpoint						X	
Other safety/tolerability			X		X		
Further endpoints						X *	
Further PK endpoints							X

* Analyses on further endpoints such as serum potassium, vital signs, and body weight, are based on TS.

6.5 POOLING OF CENTRES

This section is not applicable because centre/country is not included in the statistical model.

6.6 HANDLING OF MISSING DATA AND OUTLIERS

6.6.1 Withdrawals

The reasons for withdrawal from treatment will be reported as indicated on the electronic case report form (eCRF).

6.6.2 Efficacy data

6.6.2.1 Primary endpoint

Missing data for primary analysis will not be imputed:

- If some UACR value(s) at baseline is (/are) missing, all other available UACR samples in week -2, -1, and 0 will be used to derive UACR at baseline.
- If any UACR value after randomisation to the Treatment Period is missing, the missing UACR will not be imputed.
- UACR values excluded from the primary analysis according to the ICEs handling rules will not be imputed.

The Mixed-effect Model for Repeated Measures (MMRM) approach used for the primary endpoint (see [Section 7.4.1](#)) allows for missing data, assuming missing data following the "missing at random" assumption. Even patients with only one post-baseline assessment can be included in the model and can, therefore, contribute to the variance estimation. This primary analysis assumes that patients who had ICE(s) should have behaved similarly to those who remained in the study, and therefore is analogous to the hypothetical estimand strategy.

The table below describes how/when to derive UACR values for the statistical analysis:

Table 6.6.2.1: 1 Principal rule of First Morning Void (FMV) UACR derivation for analysis

	FMV UACR at baseline	FMV UACR at visit 8	FMV UACR at visit 9	FMV UACR at EoT
Derivation	Baseline FMV UACR is defined as the mean of all non-missing assessments from week -2 until prior to the first intake of trial medication BI 690517 or placebo in the Treatment Period.	Average of all available FMV UACR measured at visit 8 (week 6)	Average of all available FMV UACR measured at visit 9 (week 10)	EoT FMV UACR is defined as the mean of all non-missing assessments from week 12 to week 14 (EoT visit)

Sensitivity analyses will be conducted to investigate the potential effect of ICE handling approaches on the results of the primary analysis. Details about implementation of the sensitivity statistical analyses are described in [Section 7.4](#).

[figure not shown]
6.6.2.2 Secondary endpoint(s)

The principal rule of UACR derivation specified in [Table 6.6.2.1:1](#) will be used for derivation of UACR at baseline and EoT, and the UACR percent change from baseline to EoT will be calculated accordingly:

$$UACR \text{ change (\%)} = \frac{UACR \text{ at EoT} - UACR \text{ at baseline}}{UACR \text{ at baseline}}$$

Missing UACR will be imputed in the sensitivity analysis.

Details about implementation into the statistical analysis are described in [Section 7.4](#).

6.7 BASELINE, TIME WINDOWS AND CALCULATED VISITS

Section 2.2.2 of the CTP:

Throughout this protocol, the term “baseline” refers to the last observation prior to the first intake of trial medication, with the exception of FMV urine UACR. Baseline for the FMV urine UACR, is defined as the mean of all available samples from week -2 until prior to the first intake of trial medication. This does not include the UACR measured in spot urine at Screening.

Measurements taken after start of administration of trial treatment of BI 690517 will be considered on-treatment values based on the definition in [Section 6.1](#), and will be assigned to visits for statistical analysis, if applicable, as defined below.

Analysis of AE data, potentially clinically significant abnormal laboratory values, concomitant medication or non-drug therapies, as well as use of rescue therapy will not be based on visits. Therefore, no assignment to time windows will be necessary for such data.

The derivation of the last value, minimum value and maximum value of laboratory and vital signs data will consider all on-treatment values (whether or not selected in any time window; see [Section 6.1](#) for definition of the on-treatment period) within the period of interest; these will be derived for analysis of laboratory and vital signs data.

All other safety and efficacy measurements will be assigned to visits based on extended time windows around the planned visit dates, defined relative to the day of first trial treatment of BI 690517 (which is scheduled for Visit 5).

Repeated and unscheduled efficacy and safety measurements (except for laboratory data) will be handled similarly to scheduled measurements and will also be assigned to a time window depending upon the date of measurement. For handling of laboratory measurements see also [Section 7.8.2](#).

